## 4. STATISTICS

The achievement of pregnancy after diagnosis of breast cancer will be the criteria used to distinguish between two cohorts of patients: women with no subsequent pregnancies after breast cancer diagnosis (“non-pregnant cohort”), and women with one or more pregnancies any time after breast cancer diagnosis (“pregnant cohort”). Pregnancies could have resulted in live births, therapeutic or spontaneous abortions.

More than 2000 non-pregnant *BRCA* mutated breast cancer patients and more than 200 pregnant *BRCA* mutated breast cancer patients are expected to be included in the present study (estimated numbers, considering an incidence of pregnancy of approximately 10%).

To evaluate the prognostic impact of pregnancy following breast cancer diagnosis in *BRCA* mutated survivors, three survival endpoints will be considered in the two cohorts: DFS (as primary endpoint) BCSS (as secondary endpoint) and OS (as secondary endpoint). DFS event is defined by the occurrence of one of the following invasive events: local recurrence, distant metastases, contralateral or ipsilateral breast tumor, second primary malignancy, or death from any cause. BCSS event is defined as death from breast cancer. OS event is defined as death from any cause. For DFS, observation times of patients without the event will be censored on the date of their last contact. Using individual patient data from all patients included in the study, survival outcomes of patients in the

pregnant cohort will be compared to those of patients in the non-pregnant cohort. To reduce the impact of selection bias (i.e. guaranteed time bias), two analyses will be performed. In the extended Cox model analysis with occurrence of pregnancy as a time-varying covariate, all eligible patients included in the study will be considered. In the “case-control” analysis, each patient in the pregnant cohort (case) will be matched with 3 patients from the non-pregnant cohort (controls). To adjust for guaranteed time bias, each patient in the non-pregnant cohort should have a disease-free interval equal to or longer than the time elapsing between breast cancer diagnosis and date of pregnancy of the matched patient in the pregnant cohort. Patients who became pregnant after the date of the DFS event will be dropped from this analysis. Patients will be also matched according to several variables including type of *BRCA* mutation (*BRCA1* vs. *BRCA2*), hormone receptor status (positive vs. negative), nodal status (negative vs. positive), and year at diagnosis ( $\pm 2.5$  years). Because all included patients are aged  $\leq 40$  years at the time of diagnosis, matching according to age will not be performed. The matching will be done centrally at the coordinating center. Two data sets will be constituted: one for the cases and one for the potential controls. Cases will be sorted randomly and matching will be done starting for the first case until the last one. For each case, all possible controls will be extracted from the data set of potential controls. If they are only 2 controls available, matching criteria will be relaxed one by one (starting from year of diagnosis, etc) until at least a third control is found. It is anticipated, given the expected low rate of cases in the full database, to reach matching for almost each case. In these analyses, all survival endpoints will be calculated from the date of pregnancy until the date of the event. In the non-pregnant cohort, survival endpoints will be calculated from the date of diagnosis, adding the time elapsing between diagnosis and pregnancy of the matched pregnant case.

The prognostic impact (in terms of DFS, BCSS and OS) of pregnancy following breast cancer diagnosis will be then evaluated in various subgroups of *BRCA* mutated survivors according to: type of *BRCA* mutation (*BRCA1* vs. *BRCA2*), hormone receptor status (positive vs. negative), HER2 status (positive vs. negative), exposure to chemotherapy (prior exposure vs. no prior exposure), exposure to endocrine therapy (prior exposure vs. no prior exposure), interval between diagnosis and pregnancy ( $\leq 2$  years vs.  $> 2$  years after diagnosis), outcome of pregnancy (abortion vs. completed pregnancy), and breastfeeding status (breastfeeding vs. no breastfeeding).

Considering a rate of pregnancy of approximately 10%, with 2000 non-pregnant and 200 pregnant *BRCA* mutated breast cancer patients, assuming a DFS rate of 65% at 5 years in the non-pregnant cohort [21], the study will have a power of 0.83 to detect a hazard ratio of 0.75 and a power of 0.62

to detect a hazard ratio of 0.80 in favor of the pregnant cohort, at a two-sided significance level 0.05 (accrual duration 2000-2020, total study duration 2000-2030).

The rate of pregnancy following breast cancer diagnosis will be computed according to the Kaplan-Meier method. A possible increasing or decreasing trend in rate of pregnancy following breast cancer over the years will be also assessed.

The statistical analysis to evaluate the pregnancy, fetal and obstetrical outcomes of the pregnancies following breast cancer diagnosis in *BRCA* mutated survivors will be mainly descriptive and will include the following parameters:

1. Gestational age at delivery;
2. Incidence of early pre-term (< 34 weeks), late-preterm (34-36 weeks) and full-term ( $\geq$  37 weeks) pregnancies;
3. Number of pregnancies resulting in live birth and number of children born;
4. Incidence of induced and spontaneous abortion;
5. Incidence and nature of pregnancy complications (if any);
6. Incidence and nature of fetal complication and/or congenital malformations (if any);
7. Incidence and nature of obstetrical complications (if any).

To evaluate the safety of ART procedures following breast cancer diagnosis in *BRCA* mutated survivors, two groups of patients within the pregnant cohort will be considered: patients who achieved pregnancy with the use of any ART procedure (i.e. “ART group”) and patients who achieved pregnancy without the use of any ART procedure (i.e. “no ART group”). A subgroup analysis will be performed to evaluate the safety of controlled ovarian stimulation as part of ART within the ART group.

In patients who underwent chemotherapy as part of (neo)adjuvant systemic therapy, the impact of anticancer therapies (i.e. chemotherapy) on patients’ ovarian function, in terms of incidence of treatment-induced POF and age at menopause will be evaluated, if available. According to the World Health Organization definition of postmenopausal status [23], treatment-induced amenorrhea will be defined by the absence of menses for  $\geq$  12 months after the end of chemotherapy. Age at menopause will be defined as age in which patients had absence of menses for  $\geq$  12 months. For patients who

developed treatment-induced amenorrhea but then had a recovery of menses more than 12 months after the end of chemotherapy and with active menstrual function within 12 months prior to the last follow-up visit, they will not be considered as having developed menopause. Subgroup analyses will be performed according to age at diagnosis, type of chemotherapy used (anthracycline- and taxane-based regimens vs. anthracycline-based regimens vs. other regimens), and use of endocrine therapy (yes vs. no). These results will be compared to historical data in the *BRCA* wild-type breast cancer population.

Considering the sample size and the uniqueness of the young cohort of *BRCA* mutated patients expected to be included in the study, additional analyses will be conducted to describe baseline, tumor and treatment characteristics as well as patterns of care including access to risk-reducing surgeries. Possible changes over time will be also assessed. Moreover, similarly, the prognostic impact of baseline, tumor and treatment characteristics as well as of risk-reducing surgeries in *BRCA* mutated patients will be also evaluated.

In order to conduct the evaluation of TILs in this cohort, there will be no need for new cutting/preparation of tumor slides. The evaluation will be conducted on one archived diagnostic tumor-containing slide stained with hematoxylin and eosin representative of the primary tumor. The TILs scoring will be performed centrally. If available, anonymized digitally scanned images of the diagnostic hematoxylin and eosin-stained slide should be sent via email to [name] ([[contact]](mailto:[contact])) at University of Padova-Istituto Oncologico Veneto (Padova, Italy). The University of Padova-Istituto Oncologico Veneto will take care of costs related to TILs scoring and storage support (hard disk). The evaluation will be performed according to the TILs working group recommendations [24].

Patients demographic, clinical and pathologic baseline characteristics will be compared by pregnancy status using chi-square test or Fisher Exact test for categorical variables and Wilcoxon rank-sum test or t-test for continuous variables, as appropriate.

Dichotomous outcomes will be compared using univariate and multivariate logistic regression models. Time-to-event outcomes will be estimated and plotted using Kaplan-Meier methods. Survival rates will be compared using log-rank test and Cox proportional hazards models for univariate and multivariate analysis, respectively.

All tests will be two-sided and p-values of  $< 0.05$  will be considered statistically significant. All

analyses will be performed using standard available statistical programs.

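### Matched DFS analysis: controls are limited to women who never conceive, and whether a control can be reused is not stated; both tend to favour pregnancy

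*Combined protocol and SAP*

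**What the plan says.** Section 4 (Statistics) plans two analyses against guaranteed-time bias. For the first, "In the extended Cox model analysis with occurrence of pregnancy as a time-varying covariate, all eligible patients included in the study will be considered". For the second, the matched analysis, "each patient in the pregnant cohort (case) will be matched with 3 patients from the non-pregnant cohort (controls".

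The non-pregnant cohort is "women with no subsequent pregnancies after breast cancer diagnosis", so membership depends on the whole of follow-up. A control's disease-free interval must be at least as long as the case's time from diagnosis to pregnancy. The other matching factors are year of diagnosis, nodal status, hormone receptor status and *BRCA* type. On the procedure: "Cases will be sorted randomly and matching will be done starting for the first case until the last one", and "For each case, all possible controls will be extracted from the data set of potential controls". Nothing says whether a woman already chosen as a control goes back into the pool. Finally, "Patients who became pregnant after the date of the DFS event will be dropped from this analysis". The synopsis gives the same control source, interval rule and exclusion. DFS is the primary endpoint, and neither analysis is named as principal.

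**The concern.** At a case's index time, the comparison group should be every woman who is event-free, under follow-up and not yet pregnant. What happens to her afterwards should not decide whether she is eligible. Three features of the plan depart from this.

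- **Later conceivers are excluded as controls.** They are event-free up to their own pregnancy. Removing them takes event-free unexposed time out of the control group and raises its hazard, which favours pregnancy.
- **Women who conceive only after a DFS event are lost from both sides.** They are dropped as cases, and by definition they are not in the non-pregnant cohort. Their events occurred while unexposed, so losing them lowers the control hazard and partly offsets the first bias.
- **Random case order matters if controls are used once.** Women with long disease-free intervals qualify for more cases. Those taken for late pregnancies are then missing for early ones, whose remaining controls have shorter disease-free intervals. This again favours pregnancy. With reuse, case order has no effect.

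The study is meant to inform carriers about the safety of pregnancy. A shift towards apparent benefit could hide modest harm, either as the reported main estimate or as an unexplained disagreement with the Cox model.

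**Working it through.** The plan gives no figure for the bias of the matched analysis, so it was simulated under the null. The power statement in Section 4 (0.83 and 0.62) is a separate matter. Its inputs give about 1740 events and Schoenfeld power of 0.93 and 0.76, so it does not reproduce, but nothing below depends on it.

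**Inputs from Section 4.** 2000 non-pregnant and 200 pregnant women; 5-year DFS 65%, so hazard = -ln(0.65)/5 = 0.0862 per year; "accrual duration 2000-2020, total study duration 2000-2030"; testing "at a two-sided significance level 0.05", so false benefit is P(z < -1.96), nominally 2.5%; 1:3 matching on interval, year ±2.5, nodal status, hormone receptor status and *BRCA* type, relaxed from year first.

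**Assumptions not in the documents.** Intended time to pregnancy gamma with shape 2 and mean 3.5 or 5 years; data lock at 22.5 or 30 years; q, the share of intended pregnancies falling after a DFS event that still occur, 0, 0.5 or 1. There is no confounding.

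**Method.** 2200 women with diagnosis uniform over 2000-2020, true HR 1, pregnant cohort (before and after an event) set to 200, unstratified Cox model, 800 replicates in each of 12 settings. The Monte Carlo SE of the mean log HR is 0.003-0.005. Ranges run over timing and data lock.

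| Analysis | q = 0 | q = 0.5 | q = 1 |
|---|---|---|---|
| Plan, controls reused: HR | 0.968-0.988 | 0.986-0.997 | 0.995-1.005 |
| false benefit | 3.3-4.8% | 1.9-4.3% | 1.8-2.8% |
| Plan, used once, random order: HR | 0.906-0.955 | 0.941-0.975 | 0.952-0.980 |
| false benefit | 7.0-13.6% | 3.0-7.5% | 2.6-4.8% |

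Over all q, the alternatives gave:

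- risk-set controls, reused, clustered variance: HR 0.990-1.008, false benefit 1.0-3.3%;
- risk-set controls, used once, ascending interval: HR 0.991-1.007, false benefit 1.3-3.0%;
- extended Cox model: HR 0.991-1.007, false benefit 1.0-3.0%.

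**Scale.** The plan's weaker target is HR 0.80, and ln(0.80) = -0.223. At q = 0 with single use, ln(0.906) = -0.099 and ln(0.955) = -0.046, which is 44% and 21% of that distance. With reuse, ln(0.968) = -0.033 and ln(0.988) = -0.012, which is 15% and 5%.

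**More pregnancies.** The plan expects more than 200. With 300 (320 replicates), q = 0 gave 0.955-0.974 reused and 0.835-0.917 used once; q = 1 gave 0.998-1.009 and 0.931-0.975.

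**Different timing assumptions.** A second simulation (300 replicates, eight scenarios) used a constant conception hazard within a fixed window and varied follow-up, the share of women wishing to conceive, loss to follow-up and pregnancies after an event. It gave 0.94-0.98 reused, 0.83-0.94 used once in random order, 0.99-1.02 for risk-set controls with reuse, and 0.99-1.01 for the extended Cox model.

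**Separating the two mechanisms.** In five scenarios of the second simulation, never-pregnant controls used once in ascending order gave 0.94-0.98, about the same as reuse. Risk-set controls used once in random order still gave 0.89-0.97. Under single use, therefore, changing the pool alone or the order alone leaves bias behind.

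**The case against.** The strongest reply is that selection on future non-pregnancy is minor on its own. With reuse, the largest shift at 200 pregnant women is 0.033 on the log scale, against an SD of the log HR of 0.10-0.14, and at q = 1 it disappears. Taking q = 0 as typical would also be wrong: the plan itself expects pregnancies after a DFS event, and DFS events include contralateral tumours and second primaries, so q is probably above zero. The sizeable bias needs single use, which the plan does not state. The extended Cox model is already planned, and confounding by health among women who conceive could outweigh a shift of 1-3% in either analysis.

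Most of this stands. If reuse is intended, the problem is small. The Cox model is free of this particular bias, though not of confounding. Two points remain. Random ordering has little purpose if controls can be reused, which suggests single use, although that is inference. And at q = 0.5 single use still gives HR 0.94-0.98 with false benefit up to 7.5%. As written, the plan permits this version and does not prevent its HR from being reported as the main result.

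**Conclusion.** The concern holds. Followed as written, the matching rule selects controls on their future. With 200 pregnant women and a true HR of 1, the matched HR falls at about 0.97-1.01 if controls are reused and 0.91-0.98 if each is used once in random order. Reuse is close to harmless, while single use shifts the estimate towards benefit in every setting examined. The sizes rest on assumed pregnancy timing, data lock, q and constant hazards. Other timing assumptions took single use as low as 0.83, and so did 300 pregnancies (0.835 at q = 0). Only DFS was simulated; BCSS and OS were not. The problem is confined to the matched analysis and should be corrected before that analysis is run.

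**What to change.** In Section 4 and the synopsis:

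- Draw the 3 controls from all women alive, DFS-event-free, under follow-up and not yet pregnant at the case's diagnosis-to-pregnancy interval. Include women who conceive later, censored at their own pregnancy, and women who conceive only after a DFS event. Keep the other matching factors.
- State whether a control may be reused. If so, cluster the variance on the woman. If not, process cases in order of increasing interval instead of random order.

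The cost is a few lines of text and a changed matching program. The dates of pregnancy, recurrence, second cancers, death and last follow-up are already on the data collection list in Section 3.3. The downside is modest: some controls lose follow-up at their own pregnancy, and reuse needs a robust variance.

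### Pregnancy is tested within the levels of eight subgroup factors at p<0.05, with no interaction test or exploratory label, so the planned tests cannot show whether its effect differs between levels

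*Combined protocol and SAP*

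**What the plan says.** The secondary objectives (section 2, and the Synopsis) include the prognostic impact of pregnancy by BRCA type, hormone receptor status, HER2 status, chemotherapy exposure, endocrine therapy exposure, interval from diagnosis to pregnancy, pregnancy outcome and breastfeeding. Section 2 and section 4 (Statistics) write each factor as one level versus the other. Section 4 states: "The prognostic impact (in terms of DFS, BCSS and OS) of pregnancy following breast cancer diagnosis" "will be then evaluated in various subgroups of" survivors with these characteristics.

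The same section provides the methods:

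- To limit guaranteed-time bias, "two analyses will be performed": an extended Cox model with pregnancy as a time-varying covariate, and a matched comparison.
- "Survival rates will be compared using log-rank test and Cox proportional hazards models for univariate and multivariate analysis, respectively".
- On significance: "All tests will be two-sided and p-values of" less than 0.05 count as statistically significant. No result is exempted.

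The power statement covers only the overall DFS comparison, "with 2000 non-pregnant and 200 pregnant" patients, "at a two-sided significance level 0.05". Neither section 2 nor section 4 mentions an interaction or heterogeneity test, a multiplicity rule, or an exploratory status for the subgroup results. Section 4 does call the obstetric analyses mainly descriptive, but gives the subgroups no similar label.

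**The concern.** Whether pregnancy acts differently in, say, BRCA1 and BRCA2 carriers is a question about the ratio of two hazard ratios. Testing pregnancy separately in each level does not address that ratio. A level can miss p<0.05 only because it holds fewer events.

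The results would be used in counselling. Section 1 says that an earlier study with 53 pregnancies after breast cancer was too small for solid conclusions. With 200 pregnant patients, a level holding 20% of them has 40 and a level holding 10% has 20, both fewer than 53. If such a level misses p<0.05 while its counterpart reaches it, the result is easily read as a real difference in prognosis.

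**Working it through.** **Count.** 8 factors × 2 levels × 3 endpoints = 48 tests for one analysis, or 96 if both analyses are repeated in every subgroup. Section 4 does not say whether they are. If every null hypothesis held, 48 × 0.05 = 2.4 false positives would be expected.

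**Reproducing the stated power.** Inputs from section 4: 2000 and 200 patients, 65% DFS at 5 years in the non-pregnant cohort, two-sided 0.05. I assumed exponential survival and counted 10 years of follow-up for every patient.

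- Events at HR 0.75: 2000(1 − 0.65²) + 200(1 − 0.65^1.5) = 1155 + 95 = 1250.
- Power (Schoenfeld) = Φ(|ln HR| × √[d·p(1 − p)] − 1.96), with p = 200/2200 and √(1250 × 0.0826) = 10.16.
- HR 0.75: 0.2877 × 10.16 = 2.92; Φ(0.96) = 0.83. HR 0.80, with 1155 + 100 = 1255 events: Φ(0.31) = 0.62. Both agree with the plan.

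**Discordance under one common hazard ratio.** Let δ = z(power) + 1.96, which is 2.914 at power 0.83 and 2.265 at 0.62. A level holding share w of the information has power Φ(δ√w − 1.96) + Φ(−δ√w − 1.96). With level powers p₁ and p₂, the chance that exactly one level is significant is p₁(1 − p₂) + p₂(1 − p₁). The documents give no splits, so these are assumptions shown as a range.

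| Split | Level powers, HR 0.75 | Exactly one significant | Level powers, HR 0.80 | Exactly one significant |
|---|---|---|---|---|
| 50:50 | 0.54 / 0.54 | 50% | 0.36 / 0.36 | 46% |
| 70:30 | 0.68 / 0.36 | 55% | 0.47 / 0.24 | 49% |
| 80:20 | 0.74 / 0.26 | 62% | 0.53 / 0.17 | 52% |
| 90:10 | 0.79 / 0.15 | 70% | 0.58 / 0.11 | 56% |

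- No true effect: 2 × 0.05 × 0.95 = 9.5% per factor.
- Five factors on DFS, simulated as independent splits of the same patients at 50:50, 70:30 and 90:10: at least one discordant factor in 79-92% of studies under a common HR of 0.75 or 0.80, and in about 28% with no effect.
- Sensitivity: uniform accrual over 2000-2020 with follow-up to 2030 gives overall power 0.93 and 0.76 rather than the stated values. Discordance is then 43-75% per factor.

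**With an interaction test.** A uniform effect is wrongly called different 5% of the time per factor, whatever the hazard ratio. Across five factors on DFS this is about 22-23% unadjusted (1 − 0.95⁵ = 0.226).

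**Power of the interaction test.** The hazard-ratio ratio detectable with 80% power is exp[−(1.96 + 0.842) × √(1/(d·p(1 − p))) × √(1/w + 1/(1 − w))]. With 1250 events, the standard error of the overall log hazard ratio is 1/10.16 = 0.0984. At 50:50 this gives exp(−2.802 × 0.0984 × 2) = 0.58. It is 0.55 at 70:30 and 0.40 at 90:10.

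**The case against.** The strongest reply is that the plan never says subgroup differences will be judged by which level reaches p<0.05. A reader might infer this from the blanket threshold, but the documents do not state it. The objective can fairly be read as asking for level-specific estimates, and the multivariate Cox models could carry an interaction term. This stands: the defect is that no test of difference is specified. The pairing of levels still invites a contrast, and the plan offers only within-level tests to make one.

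Second, the 46-70% figures require a real, uniform benefit of the planned size, whereas section 1 frames the question largely as one of safety. That also stands, and the 9.5% figure belongs beside them. The stated powers apply to overall DFS only, so nothing here sizes the problem for BCSS or OS. The two-level formula also does not fit the three factors that exist only in pregnant patients, whose levels could share the same non-pregnant comparators.

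Third, the factors are few, prespecified and under secondary objectives, and DFS is ranked above BCSS and OS. This limits the seriousness but does not supply the missing test.

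**Conclusion.** The point holds as an omission. The plan specifies neither an interaction test nor an exploratory label, while its significance rule covers every within-level test. For a factor defined in all patients, a uniform DFS effect of the planned size would look discordant in roughly half to two-thirds of studies (46-70%), given the assumed splits and the plan's own power. With no effect the figure is about 9.5%.

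Two stronger readings are not supported. One is that the protocol prescribes inferring differences from separate p-values; that is only a likely use of its output. The other is that 48 tests make a false positive nearly certain. The 1 − 0.95^48 = 91.5% this would rest on assumes independence, but the endpoints overlap: breast cancer deaths are among all deaths, and DFS counts every death. The main defect is the missing test of difference, and multiplicity adjustment is a separate question.

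The primary DFS comparison is unaffected. The change is worth making because the subgroup results bear on counselling and the remedy is cheap.

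**What to change.** 1. For BRCA type, hormone receptor status, HER2 status, chemotherapy and endocrine therapy, fit one extended Cox model per factor and endpoint with a pregnancy-by-factor interaction. Base any claim of a difference on that term.
2. Report level-specific hazard ratios with 95% CIs, labelled exploratory, and do not call within-level results statistically significant.
3. For interval, pregnancy outcome and breastfeeding, no ordinary interaction can be fitted, because they have no value in non-pregnant patients. Compare the categories as levels of the time-varying pregnancy exposure. Each level should start only when it becomes known, for example at the end of pregnancy or the start of breastfeeding. Assigning outcome or breastfeeding from the pregnancy date would bring back guaranteed-time bias.
4. State whether subgroups are also analysed in the matched set. HER2, chemotherapy and endocrine therapy are not matching factors, so a case and her controls can fall in different levels.

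Items 1 and 2 cost SAP wording and one model term per factor. Item 3 needs recoding. Section 3.3 lists a pregnancy date and gestational age at delivery, but no separate end date for abortions and no breastfeeding start date, so some dates may have to be derived or queried. The statistical downside is low power (detectable ratio about 0.58 at a 50:50 split). The interaction tests are not themselves multiplicity-adjusted, so they too should remain exploratory.

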### Secondary objectives:

- To evaluate the prognostic impact (in terms of DFS, BCSS and OS) of pregnancy following breast cancer diagnosis in various subgroups of *BRCA* mutated patients according to:
  - Type of *BRCA* mutation: *BRCA1* vs. *BRCA2*;
  - Hormone receptor status: positive vs. negative;
  - HER2 status: positive vs. negative;
  - Exposure to chemotherapy: prior exposure vs. no prior exposure;
  - Exposure to endocrine therapy: prior exposure vs. no prior exposure;
  - Interval between diagnosis and pregnancy:  $\leq 2$  years vs.  $> 2$  years after diagnosis;
  - Outcome of pregnancy: abortion vs. completed pregnancy;
  - Breastfeeding status: breastfeeding vs. no breastfeeding.
- To evaluate the pregnancy, fetal and obstetrical outcomes of the pregnancies following breast cancer diagnosis in *BRCA* mutated patients.
- To evaluate the safety of ART procedures following breast cancer diagnosis in *BRCA* mutated patients.

- To evaluate the impact of anticancer therapies on patients' ovarian function, in terms of incidence of treatment-induced POF and age at menopause.
- To describe baseline, tumor and treatment characteristics as well as patterns of care including access to risk-reducing surgeries in *BRCA* mutated patients.
- To evaluate the prognostic impact of baseline, tumor and treatment characteristics as well as of risk-reducing surgeries in *BRCA* mutated patients.
- To evaluate tumor infiltrating lymphocytes (TILs) in *BRCA* mutated patients.

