#### 3.1. Eligibility criteria

The eligibility criteria are intentionally broad for trying to exclude as few patients as possible so that true population-based data can be obtained. To be eligible for the present study, patients should fulfill the following inclusion and exclusion criteria.

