### 3.3. Data collection

For all consecutive eligible patients included in the study from each participating Institution, their medical records will be retrieved and anonymized data entered into a database. The following information will be collected, if available:

- 1) Baseline characteristics: body mass index; smoking habit; age at menarche; age at menopause; menopausal status at the time of breast cancer diagnosis; use of birth control pills; prior children before breast cancer diagnosis; history of spontaneous abortion; history of induced abortion; prior treatment for infertility; prior gynecological surgery and/or medical history with possible impact on fertility.
- 2) Breast cancer history: date of diagnosis; age at diagnosis; disease stage; laterality of the primary tumor; type of breast and axillary surgery; use of breast reconstruction surgery; grade; histology; tumor size and nodal status (for patients who underwent primary systemic therapy, only clinical tumor size and nodal status will be collected); hormone receptor status (estrogen and progesterone receptors); HER2 status.
- 3) Treatment of the primary tumor: timing of systemic therapy administration; use of chemotherapy (type and number of cycles); use of endocrine therapy (type and duration); use of anti-HER2 targeted therapy (type and duration); use of radiotherapy.
- 4) Survival status: any recurrence of invasive breast cancer including date of the event; any second primary breast cancer including date of the event; any second primary malignancy including date of the event; date of last follow-up and/or death; cause of death (breast cancer-related or not).
- 5) Ovarian function after chemotherapy: treatment-induced POF; age at menopause.

6) Pregnancy after breast cancer: any pregnancy including date of the event; pregnancy outcome; gestational age at delivery; any pregnancy/fetal/birth complications; breastfeeding and its duration; use and type of ART.

7) BRCA mutation: date of *BRCA* testing; type of *BRCA* mutation; use and date of breast prophylactic surgery; use and date of gynecological prophylactic surgery.

8) Additional information: diagnosis of breast cancer during pregnancy, availability of digital scanned images for TILs analysis

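### The endocrine-therapy subgroup is not limited to hormone-receptor-positive disease, so its unexposed stratum will be mostly receptor-negative and its result is confounded with the receptor-status subgroup

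*Combined protocol and SAP*

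**What the plan says.** The secondary objectives in Section 2 list the subgroup as "Exposure to endocrine therapy: prior exposure vs. no prior exposure", and Section 4 repeats it as "exposure to endocrine therapy (prior exposure vs. no prior exposure"). Neither place limits it by receptor status. The same list has a separate factor, "Hormone receptor status: positive vs. negative".

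Eligibility has no receptor criterion, and Section 3.1 explains that "The eligibility criteria are intentionally broad for trying to exclude as few patients as possible". Section 3.3 collects both variables: "hormone receptor status (estrogen and progesterone receptors") and "use of endocrine therapy (type and duration").

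In the matched analysis of Section 4, receptor status is one of the matching factors: "hormone receptor status (positive vs. negative), nodal status (negative vs. positive), and year at diagnosis". Endocrine exposure is not. Section 4 also mentions multivariate Cox models, but lists no covariates and no interaction term.

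**The concern.** Endocrine exposure and receptor status are closely tied. A receptor-negative woman is likely to be unexposed because of her tumour type. A receptor-positive woman is unexposed for some other reason. The split as written pools the two.

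Suppose the pregnancy hazard ratio differs between exposed and unexposed women. A reader will want to link that difference to endocrine treatment, because that is how the subgroup is named. The same difference would appear if the effect of pregnancy varied only by receptor status and endocrine therapy played no part. The receptor subgroup already addresses that second question, so the endocrine subgroup would add little and could mislead.

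**Working it through.** **Inputs.** The documents state neither the receptor-positive share nor the uptake of endocrine therapy. Assumptions:
- p, receptor-positive share: 0.3 to 0.7
- u, uptake among receptor-positive women: 0.60 to 0.95
- uptake among receptor-negative women: none

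The sample size (2000 non-pregnant, 200 pregnant), 65% DFS at 5 years, two-sided 0.05 and the power figures come from Section 4.

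**Step 1: the plan's own figure.** There is none for this subgroup, so the stated overall power serves to calibrate the event count. Take exponential DFS and 10 years of follow-up for every patient. Non-pregnant DFS at 10 years is 0.65² = 0.4225, and at HR 0.75 pregnant DFS is 0.4225^0.75 = 0.524. Events: 2000 × 0.5775 + 200 × 0.476 ≈ 1250. Schoenfeld power is Φ(√(d·a(1−a))·|ln HR| − 1.96) with a = 200/2200. This gives 0.83 at HR 0.75 and, with 1255 events, 0.62 at HR 0.80. Both match the plan.

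**Step 2: make-up of the unexposed stratum.** Receptor-negative share = (1−p) / [(1−p) + p(1−u)].

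| p | u = 0.60 | u = 0.80 | u = 0.90 | u = 0.95 |
|---|---|---|---|---|
| 0.3 | 85% | 92% | 96% | 98% |
| 0.5 | 71% | 83% | 91% | 95% |
| 0.7 | 52% | 68% | 81% | 90% |

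Receptor-negative women are the majority throughout. The margin is thin at p = 0.7, where a majority needs uptake above 1 − 0.3/0.7 = 57%. If 5% of receptor-negative women were treated, the lowest cell becomes 0.285/(0.285 + 0.28) = 50.4%.

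A share of 90% needs u ≥ 1 − (1−p)/(9p): 74% at p = 0.3, 89% at p = 0.5 and 95% at p = 0.7.

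**Step 3: overlap with the receptor subgroup.** The two splits disagree only for untreated receptor-positive women, a fraction p(1−u). They classify 1 − p(1−u) of patients the same way: 1 − 0.28 = 72% at p = 0.7, u = 0.60, and 1 − 0.015 = 98.5% at p = 0.3, u = 0.95.

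**Step 4: what this does to the comparison of strata.** Let the log hazard ratio for pregnancy be A in receptor-positive and B in receptor-negative disease, with no role for endocrine therapy. The exposed stratum estimates A. If pregnancy and event rates are similar across groups, the unexposed stratum estimates roughly wB + (1−w)A, where w is the share in Step 2. The apparent difference by endocrine exposure is about w(B − A). So roughly 52-98% of any receptor difference would show up as an endocrine difference. Within receptor-positive patients it would be zero.

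**Step 5: numbers after restriction.** With equal pregnancy and event rates across groups, unexposed receptor-positive pregnant patients number 200·p·(1−u), and events are 1250·p·(1−u). Power is at HR 0.75.

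| p, u | Exposed: pregnant / events / power | Unexposed: pregnant / events / power |
|---|---|---|
| 0.5, 0.80 | 80 / 500 / 0.46 | 20 / 125 / 0.15 |
| 0.5, 0.90 | 90 / 563 / 0.50 | 10 / 63 / 0.10 |
| full range | 36-133 / 225-831 / 0.24-0.66 | 3-56 / 19-350 / 0.055-0.34 |

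**The case against.** The strongest reply is that the planned comparison is pregnant against non-pregnant within each stratum, not exposed against unexposed. The objective asks for the impact of pregnancy in subgroups and does not claim that endocrine therapy modifies it. Receptor status is a matching factor, which works against receptor imbalance between cases and controls. This stands in part: the confounding arises when the two stratum results are set beside each other. That comparison is the usual purpose of a subgroup factor, however, and matching does not address it. Matching also balances receptors overall, not within exposure strata. As an assumed illustration, let half the patients be receptor-positive, with uptake of 90% in non-pregnant and 60% in pregnant women. The unexposed stratum is then 91% receptor-negative among non-pregnant and 71% among pregnant women. The extended Cox analysis is unmatched, and no stated covariate covers the gap.

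A second reply is that restriction leaves the exposed stratum largely as it was and makes the unexposed one very small, so the study still could not settle whether endocrine treatment matters. That is correct, and it limits what the fix can promise.

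A reader might also infer that the unexposed stratum is nearly all receptor-negative and that the analysis simply repeats the receptor subgroup. The documents do not support that. They give none of the inputs, and at the low end of the range close to half of the stratum is receptor-positive.

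**Conclusion.** The concern holds as one of confounding and substantial overlap. The subgroup is defined over all patients, and nothing in the plan separates endocrine exposure from receptor status. Under the assumed ranges and no treatment of receptor-negative women, the unexposed stratum is 52-98% receptor-negative. A difference in the pregnancy effect between exposure strata could not be attributed to endocrine therapy.

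The reach is limited. This is one of eight secondary subgroup factors. It would be wrong to infer that the primary DFS comparison is compromised, or that information is lost, since both variables are collected. It is a cheap improvement.

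**What to change.** In Sections 2 and 4, define the endocrine-therapy subgroup within hormone-receptor-positive patients. The plan already restricts another analysis by relevant treatment: the ovarian-function evaluation is done "In patients who underwent chemotherapy as part of (neo)adjuvant systemic therapy".

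State the date up to which exposure counts: the pregnancy date in cases and the matched time in controls. The listed endocrine fields are type and duration, so check how far they support this dating. The extended Cox analysis has no matched time, so the text should say how exposure is dated there. The receptor restriction does not depend on either answer.

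Report the cross-table of receptor status by endocrine exposure, separately for pregnant and non-pregnant patients, and label the subgroup result descriptive.

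The cost is a phrase in two places and one table. The price in precision is a small unexposed group with wide intervals, which reflects the information the study actually has on this question.
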